12.2. Adequacy of protection against risks

The parent MESA study has Institutional Review Board (IRB) approval from each field site and from the University of Washington, which is the Data Coordinating Center. All MESA participants provided informed consent at the time of initial enrollment in 2000-2002. At Exam 6, study personnel will approach MESA participants for potential inclusion into this ancillary study. Interested and eligible participants will be provided with adequate time and privacy to undergo the informed consent process.

Data management and security will be handled by the MESA Data Coordinating Center at the Center for Collaborative Studies (CHSCC) at the University of Washington. Only CHSCC staff has access to the Coordinating Center's personal computers, simplifying security arrangements. Access is protected by individual unit keys to prevent tampering or unauthorized access to the units. Use of a Local Area Network (LAN) provides two additional levels of security in the unlikely event of an unauthorized user finding a machine unattended or unlocked. The LAN restricts access to the Database files via passwords, and the Database itself requires a password before files may be opened. All data transmissions occur without accessing unique identifiers. A master file that matches identification numbers with information that identifies an individual is maintained at the CHSCC, and is not accessible to study investigators.

Potential benefits of the proposed research to study participants and others

Vitamin D may help reduce the risks of cardiovascular disease and other chronic medical conditions. However, substantial variability in the biological response to vitamin D among individuals is suspected from previous studies and understanding of vitamin D metabolism. Defining individual-level determinants of vitamin D treatment response may facilitate a “personalized medicine” approach to vitamin D treatment, in which long-term therapy is effectively targeted to patients who are most likely to derive clinical benefit. We believe that the overall benefits of this trial outweigh the risks to participants, because the risk to participants is minimal, and because the potential benefits of lowering cardiovascular risk in the general population are significant. We believe that a placebo group is justified because the clinical benefits of vitamin D supplementation are still undergoing evaluation in clinical trials that will not report results for several years and the proposed duration of treatment is short (16 weeks).

After completing participation in MESA INVITE, each participant will receive his or her serum 25-hydroxyvitamin D concentrations, measured from serum drawn at both Exam 6 and Exam 6a. They will also receive their treatment assignment (placebo or 2000 IU vitamin D₃ daily) to help interpret their laboratory values. The 25-hydroxyvitamin D measurements will be performed in a CLIA-supervised laboratory supervised by [name] and calibrated to NIST standards. The 25-hydroxyvitamin D measurements will thus be suitable for use by participants and their healthcare providers to make future decisions regarding non-study vitamin D supplementation.

Importance of the knowledge to be gained

Cardiovascular disease is a leading cause of death in the United States, and is responsible for more than 16 million annual deaths worldwide. This trial focuses on a promising therapy that may help to reduce the risk of cardiovascular disease. We anticipate this trial will help identify characteristics that predict the biological response to vitamin D treatment, which is currently undergoing evaluation in trials and increasingly used in clinical practice. This trial is intended to generate new knowledge regarding how current and future vitamin D therapies could be used.

ANALYTIC PLAN

Changes to recruitment, analysis, and sample size in response to the low accrual of research participants for R01 HL096875-07: Individual Response to Vitamin D Treatment (INVITE)

Brief statement of the problem

The Individualized Response to Vitamin D Treatment (INVITE) trial was designed to identify clinical, genetic, and biomarker differences across individuals in response to cholecalciferol therapy. The trial was originally conceived to address two emerging research directions within the National Heart Lung and Blood Institute (NHLBI):

1. Innovative use of existing observational cohort studies to include nested clinical trials
2. A personalized medicine approach that includes testing individualized responses to treatments, including clinical and genetic characteristics.

The INVITE trial is nested within the NHLBI sponsored Multi-Ethnic Study of Atherosclerosis (MESA). Participants are recruited from four MESA clinical sites at the time of their 6th examination. Recruitment for the INVITE trial has been lower than anticipated due to:

[figure not shown]
1. Overall turnout for MESA Exam 6 was considerably lower than expected, particularly at the Wake Forest site, which is a primary INVITE recruitment site.
2. The INVITE grant was funded after MESA Exam 6 was already underway.
3. The use of high-dose cholecalciferol supplementation was greater than expected.

We have implemented several procedures to increase recruitment, including the creation of specialized visits for participants who already completed MESA Exam 6, the inclusion of an optional washout period for pre-existing vitamin D users, and the addition of a 5th MESA recruitment site. Each of these procedures have increased enrollment; however, the final anticipated sample size will be 682.

Changes to enrollment

As of September 1, 2018, the MESA INVITE study had enrolled 523 participants. We now plan to enroll 682 participants by January 18, 2019, at which time we will close enrollment. We are currently on track to meet this goal based on the current rate of recruitment (below). With 16 weeks of scheduled follow-up for each participant, we plan to complete all study visits by May 30, 2019.

Figure 1. Enrollment in MESA INVITE

Changes to the analytic plan

The overall design of the study has not changed. INVITE remains a randomized two-arm, double-blind clinical trial with a 3:1 ratio of assignment to active vitamin D treatment versus placebo. We discussed the possibility of removing the placebo group to create a treatment only study; however, implementing such a change after recruitment of greater than 75% of participants would be difficult to explain to the DSMB, the MESA study sites, and the participants themselves. Moreover, we believe that such a change in design would diminish the impact of manuscripts resulting from this study.

Unlike typical event driven trials, INVITE seeks to identify characteristics that modify the response to treatment. To increase study power to detect such associations, we will start by evaluating only participants who are treated with active vitamin D to assess main effects of genetic polymorphisms and clinical characteristics on the changes in study outcomes. In parallel we will present analytic results from our original approach, in which we analyze all participants and test the interaction of relevant exposures with treatment assignment.

Changes to sample size and study power

Study power for the treatment only analytic approach is considerably greater than that of the original interaction-based analyses. Differences in the effect of vitamin D treatment on study outcomes of change in parathyroid hormone, 1,25-dihydroxyvitamin D, and urine calcium to creatinine ratios according to a modifying genetic polymorphism are presented below. Under the anticipated sample size of 682, the INVITE study will maintain power to detect clinically relevant associations. The INVITE DSMB, which includes a faculty biostatistician, met on September 13, 2018, at which time it reviewed and approved these changes to the analytic plan and power.

Figure2. Minimal detectable associations for genetic polymorphisms under a treatment-only analysis.

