	Exclusion criteria 
1. Current use of >1,000 international units (IU) of cholecalciferol daily2. Current use of any activated vitamin D product (calcitriol, paricalcitol, hectorol)3. Known history of allergy or adverse reaction to vitamin D treatment4. Known clinical history of primary hyperparathyroidism5. Known clinical history of kidney stones within the previous 5 years6. Known clinical history of kidney dialysis or transplant.7. Known clinical history of sarcoidosis8. Self-reported history of having elevated serum calcium levels9. Serum calcium level >11 mg/dl at MESA Exam 1 (2000-2002)10. Current participation in another interventional study11. Inability to provide written informed consent
Study Duration	16 weeks
Treatment, Dosage, and Route of Administration	2,000 IU cholecalciferol or inactive placebo taken by mouth once daily
Efficacy Assessments	Change in serum 1,25-dihydroxyvitamin D concentration, serum parathyroid hormone concentration, and blood pressure from baseline to 16-week follow-up visit.

Safety Assessment	Change in urine and serum concentrations of calcium and phosphate from baseline to 16-week follow-up visit. Research staff will assess adverse effects during the study duration by participant self-report.
Modifying Characteristics	The following characteristics will be evaluated for their influence on the biological response to cholecalciferol treatment: genetic polymorphisms, serum concentrations of vitamin D metabolic markers, race, gender, and body mass index.
Statistical Methods	Linear models will be constructed for the follow-up value of each outcome variable. Models will include the initial value of the outcome variable, treatment assignment, and the interaction of treatment with the potential modifying variables.
Date of protocol	February 5, 2018

ABBREVIATIONS

MESA = Multi Ethnic Study of Atherosclerosis

1,25(OH)₂D = 1,25-dihydroxyvitamin D, the activated form of the hormone

25(OH)D = 25-hydroxyvitamin D, the accepted marker of vitamin D storage

Vitamin D₃ = cholecalciferol, the active treatment in the study

PTH = parathyroid hormone

IU = international units

UV = ultraviolet

AE = Adverse event

SAE = Serious adverse event

GFR = glomerular filtration rate

CHSCC = Collaborative Health Studies Coordinating Center

NORC = Nutrition and Obesity Research Center

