10. ANALYTIC PLAN

We will describe MESA participants screened, enrolled, and completing this ancillary study according to CONSORT guidelines and compare characteristics of participants who do and do not pass through each of these stages. Primary analyses will include participants who complete baseline and 16-week follow-up regardless of adherence. Secondary analyses will include all consented participants using multiple imputation to address data missing from the 16-week follow-up visit.

We will construct linear models for the follow-up value of each outcome variable to determine whether common and rare polymorphisms in six candidate genes modify vitamin D₃ treatment effects: *CYP2R1*, *CYP24A1*, *CYP27B1*, *CYP3A4*, *SULT2A1*, and *VDR*. Independent variables in the model will include treatment group, number of minor alleles at a given locus, the interaction between treatment group and number of minor alleles, the baseline value of the outcome variable, and the following preselected precision variables: age, gender, BMI, season, and the estimated glomerular filtration rate (GFR). Given sample size limitations we will conduct primary genetic analyses among only the white and Black subgroups with potential associations carried to the Chinese and Hispanic groups. Power to detect genetic associations of common variants are shown in Table 1. Secondary genetic analyses are planned to explore all measured and imputed genetic variants with >5% minor allele frequency derived from the Affymetrix 6.0 chip and 1000 Genomes imputation using the regression framework described above.

Table 1. Power for analyses of common variants.

Minor allele frequency	All	White	Black
0.1	0.013	0.001	0.001
0.2	0.141	0.013	0.006
0.3	0.357	0.045	0.021
0.4	0.521	0.083	0.041

We will test whether race/ethnicity, gender, body mass, index, estimated GFR, and serum concentrations of 25(OH)D, bioavailable 25(OH)D, and 24,25(OH)₂D₃ modify the response to vitamin D₃ treatment using analogous regression models to those described above.

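### The SAP leads with active-arm associations and words their power as differences in vitamin D effect, without saying that claims of modification rest on the parallel interaction test

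*Combined protocol and SAP*

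**What the plan says.** Section 2 of the protocol gives the primary aim as finding polymorphisms, clinical characteristics and biomarkers that modify the biologic response to vitamin D₃. The Protocol Summary specifies the model for this: "Models will include the initial value of the outcome variable, treatment assignment, and the interaction of treatment with the potential modifying variables". Section 10 repeats it for genotype ("We will construct linear models for the follow-up value of each outcome variable", with treatment, allele count, their interaction and the baseline value) and uses analogous models for race/ethnicity, gender, BMI, eGFR and vitamin D metabolites.

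The SAP that follows the protocol keeps the 3:1 placebo-controlled design but reduces the expected sample from 1,600 to 682. To gain power, it says "we will start by evaluating only participants who are treated with active vitamin D to assess main effects of genetic polymorphisms and clinical characteristics", with changes in the outcomes as the response. It then adds: "In parallel we will present analytic results from our original approach, in which we analyze all participants and test the interaction".

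Under Changes to sample size and study power it says: "Study power for the treatment only analytic approach is considerably greater than that of the original interaction-based analyses". The sentence introducing Figure 2 names the plotted quantity "Differences in the effect of vitamin D treatment on study outcomes of change in parathyroid hormone" and two further outcomes, according to a modifying polymorphism. The caption of that figure reads "Minimal detectable associations for genetic polymorphisms under a treatment-only analysis". Between the two stands the conclusion: "Under the anticipated sample size of 682, the INVITE study will maintain power to detect clinically relevant associations".

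No section says which of the two analyses supports a claim of modification, or what to conclude if they disagree. No readable text gives interaction power at N=682.

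**The concern.** A main effect among treated participants and a treatment-by-characteristic interaction are different quantities. The first includes whatever association the characteristic would have had with the outcome on placebo. The plan's own text gives a reason not to take that association as zero. Race/ethnicity is a planned modifier, and the Introduction reports that 1,25(OH)₂D, one of the outcomes, is higher in African Americans, without reference to treatment. That is a difference in level, so its relevance depends on how the treated-only model handles baseline.

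Two things are at stake. A characteristic that only predicts the outcome could be reported as modifying the response to vitamin D. And readers could take the treated-only detectable effects as detectable modification, for which 682 participants give much less power.

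**Working it through.** **Inputs from the documents.** N=682 and 3:1 allocation (SAP), hence 511.5 and 170.5 expected, taken as 512 active and 170 placebo. Planned N=1,600 (Section 3), hence 1,200 and 400. African American share 36% (Section 12.1), used as an illustrative prevalence. Section 5 expects larger variability in the active arm but gives no figure.

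**Assumptions, not in the documents.** Two-sided alpha 0.05; 80% power; stable level difference d = 0.2 to 0.5 SD; slope r of follow-up on baseline = 0.6 to 0.8; ratio v of placebo to active residual variance = 1 or 0.5; no missing follow-up.

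**The plan's own figures.** Figure 2 is not shown, so there is no numeric power at N=682 to reproduce. The statement that over 75% had been recruited agrees with 523/682 = 76.7%. The direction of the stated power comparison is confirmed in step 3.

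**1. What each analysis estimates.** Let X be the characteristic and T treatment, with model terms βx·X and βtx·T·X. The placebo slope is βx and the active slope is βx + βtx. The treated-only slope equals the modification βtx only if βx = 0.

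**2. False positives with βtx = 0.**

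*Baseline-adjusted follow-up model.* If X shifts the outcome by d at both visits, the coefficient of X is d − r·d = (1 − r)d in each arm. For d=0.3 and r=0.6/0.7/0.8 this is 0.12/0.09/0.06. Simulated means were 0.124/0.090/0.058 in the active arm and 0.122/0.088/0.062 in the placebo arm, so the interaction cancels it. Check of one cell (d=0.3, r=0.7): SE = √(1 − 0.49)/√(512 × 0.36 × 0.64) = 0.714/10.86 = 0.066; 0.09/0.066 = 1.37; rejection ≈ Φ(1.37 − 1.96) ≈ 28%, against 26.3% simulated.

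Simulated treated-only rejection (3,000 trials per cell):

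| d | r=0.6 | r=0.7 | r=0.8 |
|---|---|---|---|
| 0.2 | 19.0% | 14.9% | 10.3% |
| 0.3 | 38.3% | 26.3% | 17.3% |
| 0.5 | 74.1% | 59.7% | 42.0% |

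The interaction test on the same data, with equal variances, rejected in 3.7% to 6.1%. At alpha 0.001 the treated-only rates for d of 0.2 and 0.3 were 0.6% to 5.3%.

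*Change-score model.* A stable d cancels. Treated-only rejection was 4.3% to 5.3% in all nine cells (4,000 trials each).

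*Change related to X in both arms.* Change scores do not remove this. With an allele at frequency 0.3 shifting change by 0.10/0.15/0.20 SD per allele in both arms, the treated-only test rejected in 31%/59%/84% and the interaction test in 4.7%/5.8%/4.8% (4,000 trials each).

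**3. Precision, equal variances** (in units of residual SD divided by the SD of X).
- Treated-only, N=682: 1/√512 = 0.0442
- Interaction, N=682: √(1/512 + 1/170) = 0.0885
- Interaction, N=1,600: √(1/1200 + 1/400) = 0.0577

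Ratios: 0.0885/0.0442 = 2.0; 0.0885/0.0577 = 1.53; 0.0442/0.0577 = 0.77. The treated-only analysis at 682 is more precise than the interaction was at 1,600; the interaction itself is less precise by a factor of 1.53.

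**4. Power.** An effect with 80% treated-only power lies 1.96 + 0.84 = 2.80 standard errors from zero. As an interaction with v=1: Φ(2.80/2.0 − 1.96) ≈ 29%. With v=0.5 and arm-specific variances the SE ratio is √(1 + 3 × 0.5) = 1.58, and Φ(2.80/1.58 − 1.96) ≈ 43%. With v=0.5 and a pooled variance it is again about 29%.

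**5. Detectable effect, 36% prevalence, 80% power.** √(0.36 × 0.64) = 0.48. Treated-only: 2.80 × 0.0442/0.48 = 0.26 residual SD. Interaction: 2.80 × 0.0885/0.48 = 0.52. With v=0.5 the interaction figure is 0.41 with arm-specific variances and 0.46 with a pooled variance.

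**The case against.** Much of what is needed is already in the documents. Section 10 ties modification to the interaction term, and the SAP keeps the placebo arm, commits to presenting the interaction test and says openly that it has less power. The Figure 2 caption is correctly labelled, and the power conclusion speaks of associations. The DSMB, with a biostatistician, approved the change. A reader who infers that the interaction analysis was dropped would be wrong. What remains is still a gap: the lower-powered test has no stated inferential role, disagreement between the analyses is likely, and the sentence introducing Figure 2 conflicts with its caption. DSMB approval does not settle either.

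A second objection stands in full. A reader might infer that the plan carries a false-positive rate of up to 75%. It does not follow. The SAP speaks of changes in outcomes and Section 7 defines the outcomes as changes. On a change-score reading, a stable level difference does no harm. The high rates need the baseline-adjusted model of Section 10, carried over without its treatment terms, and an alpha of 0.05 that the documents do not state. For the same reason, prescribing a baseline-adjusted treated-only model would be no remedy, since that model creates the artefact.

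It is also tempting to rescale Table 1 of Section 10 to N=682. The table gives no alpha or effect size, so this is not supported. Nor can the values in Figure 2 be called wrong, since the figure cannot be seen.

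**Conclusion.** The concern holds as a gap in interpretation and in the wording of power. Followed as written, the plan lets an on-treatment association be reported as modification, because the condition of no association under placebo is not stated and the interaction test has no deciding role. How often this would mislead cannot be fixed from the documents. Under the assumptions above it ranges from about 5% (change score, stable level difference) to about 75% (baseline-adjusted, 0.5 SD), and it exceeds 5% under either model if the characteristic predicts change on placebo.

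The power result is firmer. With equal variances the factor of 2.0 follows from 3:1 allocation alone, whatever the alpha or allele frequency. Power described as maintained at N=682 is therefore supported for treated-arm association only. For modification, 80% becomes about 29% with equal variances, or about 43% if placebo variance is half the active variance and arm-specific variances are used.

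**What to change.** 1. Under Changes to the analytic plan, state that claims of modification rest on the treatment-by-modifier estimate and its interval in all randomised participants. Label the treated-only results as on-treatment associations or as a screen.
2. Under Changes to sample size and study power, reword the sentence introducing Figure 2 so that its power refers to association within the treated arm. Add the interaction test's detectable effect at N=682, with its alpha and variance assumption. An example for a 36% characteristic at 80% power and alpha 0.05 is about 0.52 residual SD, against 0.26 treated-only, with equal variances.
3. Optional: use robust or arm-specific variances for the interaction, given the unequal variability that Section 5 expects. This is a matter of efficiency only. At v=0.5 the pooled test is conservative (1.4% to 2.3% rejection at nominal 5%).

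The cost is a few sentences and one power line. Both analyses are already planned and no new data are needed. The downside is a less favourable stated power for the trial's main question.
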